
Section 12.1.11 Pregnancy and Follow-Up
	
Pregnancies are not considered AEs in and of themselves; however, if a female study participant becomes pregnant while she is enrolled in the clinical study, she must discontinue investigational product 8.4.1.3 and the Sponsor must be notified within 24 hours of the Investigator’s learning of the pregnancy by completing the Pregnancy Notification Form and faxing or emailing to the Sponsor at [contact] or [contact].
 
Safety will be monitored and assessed by AEs/SAEs, medical history, physical examination, vital signs measurements, ECG results, and clinical laboratory assessments. The Sponsor may also follow the health of an infant born subsequent to use of investigational product.
 
The subject may reinstate investigational product after delivery and cessation of breastfeeding (if applicable) at the discretion of the Investigator.
	
Pregnancies are not considered AEs in and of themselves; however, if a female study participant becomes pregnant while she is enrolled in the clinical study, she must interrupt treatment with investigational product immediately (see Section 8.4.1.3) and the Sponsor must be notified within 24 hours of the Investigator’s awareness of the pregnancy by completing the Pregnancy CRF in the EDC system and downloading and completing the Pregnancy Report Form. The Pregnancy Report Form must be emailed to [contact] or faxed to [contact]. The subject and neonate must be followed for outcome information and/or as considered appropriate by the Investigator and Sponsor.
 
The subject may restart investigational product when she is no longer pregnant or
	
Updated to align with modified standard safety procedures and Sponsor standard language.

Section	Original Text (Amendment 3, 07 September 2016)	Revised Text (Version 4, 10 May 2017)	Justification for Change								
	
Subjects whose pregnancy is terminated early (planned or unplanned) may be permitted to resume participation in the study if termination of the pregnancy is confirmed by a serum β-hCG test (see Section 8.4.1).
	
breastfeeding (if applicable) at the discretion of the Investigator and after discussion with the Medical Monitor. The subject must have a negative pregnancy test before restarting investigational product. If a subject's pregnancy is terminated early (planned or unplanned), she must have termination of the pregnancy confirmed by a serum β-hCG test before restarting investigational product.
 
Completing the Pregnancy Report Form is not a substitute for reporting an AE/SAE when and AE/SAE has occurred. In the situation when an AE/SAE has occurred, the AE/SAE reporting procedures described in Section 12.1.5 must also be followed.
									

Section 12.2.7 Laboratory Assessments
	
The list of laboratory analytes to be tested is shown in Table 10.
	
The list of laboratory analytes to be tested is shown in Table 11, and the normal reference ranges for liver biochemistries are shown in Appendix C.
	
Added per Regulatory Authority request.
								

Section 12.2.7 Table 10 List of Laboratory Analytes
	
 
 Measurement of Liver Fibrosis	Fibroscan	
 
 Bone Density Assessment	DEXA	
 
 Other	Insertion	
 
	Measurement of Liver Fibrosis	Fibroscan	Bone Density Assessment	DEXA	Other	Insertion	
Deletion
 
 
 Other	OCA-glucuronide	
 
	Other	OCA-glucuronide	
Measurements of liver fibrosis are captured in a different section.
 
OCA-glucuronide was listed in the text but missing from the table.

Measurement of Liver Fibrosis	Fibroscan										
Bone Density Assessment	DEXA										
Other	Insertion										
Other	OCA-glucuronide										

Section 13 Statistical Methods
	
A statistical analysis plan (SAP), providing details about the specific planned analyses and hypothesis tests, will be prepared and approved by the Sponsor and its designees prior to study database lock, propensity score determination, and unblinding of the double-blind subject treatment assignments.
	
A statistical analysis plan (SAP), providing details about the specific planned analyses and hypothesis tests, will be prepared and approved by the Sponsor and its designees prior to the first interim analysis, propensity score determination, and unblinding of the double-blind subject treatment assignments.
	
Reflects addition of interim analyses to the study protocol.
								

Section	Original Text (Amendment 3, 07 September 2016)	Revised Text (Version 4, 10 May 2017)	Justification for Change

Section 13.1.1 Analysis Populations
	
• The Randomized Population will include all randomized subjects
 
Insertion
	
Deletion
 
 • The Per Protocol (PP) Population will include all ITT subjects who do not have any major protocol violations that potentially affect the efficacy conclusion. Treatment assignment will be based on the randomized treatment. 	
Rationale 12

Section 13.1.1.1 Comparability of Historical Controls
	
Historical controls from both databases will be chosen based on the same study inclusion/exclusion criteria where possible.
	
Historical controls from both databases will be chosen based on the same study inclusion/exclusion criteria. Propensity score matching method will be utilized to select historical controls that match the treated subjects using available covariates. The adequacy of matching will be assessed by statistical methods described under Section 13.1.8.
	
Clarifies the use of propensity scores in the assessment of the historical control population.


Section 13.1.2.1 Sample Size Monitoring
	
13.1.2.1 Sample Size Re-Estimation Plan Therefore, starting approximately 2 years after the first subject is randomized, the aggregate event rate and sample size based on recruitment and retention will be evaluated in a blinded manner quarterly. This evaluation will determine if any increases in number of subjects are required in order to obtain a total of 121 adjudicated events for the final analysis in the combined groups. If after 4 years of accruing subjects, despite increases in the number of subjects, it is determined that at least an additional 2 years (ie, total study duration of at least 10 years) are needed to randomize sufficient subjects to achieve a total of 121 adjudicated events, all subjects enrolled from that point forward will receive open label OCA. Previously randomized subjects will
	
13.1.2.1 Sample Size Monitoring Therefore, the aggregate event rate and sample size based on recruitment and retention will be evaluated in a blinded manner quarterly. This evaluation will determine if any increases in number of subjects are required in order to obtain a total of 127 adjudicated events for the final analysis in the combined groups.
 
Deletion
	
Clarifies the ongoing monitoring of event rate and sample size.

Section	Original Text (Amendment 3, 07 September 2016)	Revised Text (Version 4, 10 May 2017)	Justification for Change
	
continue to be treated in a blinded manner with either OCA or matching placebo. If this modification is implemented, the alternative primary efficacy analysis is specified in Section 13.1.9.
 
Any revised sample size or changes to treatment allocation will be justified and documented in a protocol amendment and in the CSR.
		

Section 13.1.5.1 Association of Biochemistry with Clinical Outcomes and Clinical Benefit
	
Insertion (new subsection)
	
13.1.5.1 Association of Biochemistry with Clinical Outcomes and Clinical Benefit The association between biochemistry including ALP and bilirubin with clinical outcomes will be assessed and the clinical benefit of OCA using biochemistry as a surrogate endpoint will be evaluated. Detailed analysis will be described in the SAP. Based on the association between biochemical changes and clinical outcomes described above, clinical benefit of OCA using biochemistry as a surrogate endpoint for key subpopulations of interest will be evaluated. This analysis will be further described in the SAP.
	
This analysis will provide additional insight into the connection between surrogate endpoints and clinical outcome events allowing for evaluation of benefit in subpopulations for which the study is not powered.

Section 13.1.8 Supportive Analysis
	
In order to address the risks associated with the inclusion of a long-term placebo arm, supportive analyses of the primary endpoint will compare clinical outcomes in the OCA treatment arm to historical controls.
 
By comparing how outcomes differ for treated subjects relative to historical controls, it is possible to estimate the effects of the treatment.
	
In order to address the risks associated with the inclusion of a long-term placebo arm, supportive analyses of the primary endpoint will compare clinical outcomes in the OCA treatment arm to historical controls, which serves as an external control for supportive analysis.
 
By comparing how outcomes differ for treated subjects relative to historical controls, it is possible to estimate the effects of the treatment between the treated subjects and the matched natural history subjects.
	
Clarifies the use of the historical controls as an external control in supportive analyses of the primary endpoint and clarify the process for selecting the comparator group for the primary efficacy analysis using propensity score analysis.

Section	Original Text (Amendment 3, 07 September 2016)	Revised Text (Version 4, 10 May 2017)	Justification for Change
	
Although it might be relatively simple to assign a historical control based on a single observable characteristic, in practice, if the matching process is to successfully mitigate potential bias, it has to be done considering a full range of covariates across which the treatment and historical controls might differ.
 
Only covariates and not outcome variables will be included in the propensity score estimation. Therefore, there is no chance of biasing to avoid biased results that are in favor of one treatment.
 
The propensity score quintile will be then be used as the stratification factor in the stratified log rank test to compare randomized OCA-treated subjects in the ITT population and historical controls (Overall Historical Control Population: both the UK-PBC Group and Global PBC Study Group databases) on the following outcomes:
	
A full range of covariates across which the treatment and historical controls might differ will be considered to mitigate potential bias.
 
Only covariates and not outcome variables will be included in the propensity score estimation to avoid biased results that are in favor of one treatment.
 
The baseline characteristics between treated and natural history subjects in the matched dataset will be summarized and presented in a tabular format. Statistical methods such as Wilcoxon Rank-Sum test will be used to assess the balance for baseline covariates. The standardized difference and variance ratios for these covariates will also be calculated. In addition, box plots of propensity scores for treated and natural history subjects will be separately presented, to further assess the adequacy of matching.
 
A third-party statistician(s) will perform the propensity score modeling and matching. This third-party statistician(s) will be separate and independent from the statistician(s) who will assess the success of matching and perform efficacy analyses.
 
The propensity score quintile will be then be used as the stratification factor in the stratified log rank test to compare randomized OCA-treated subjects in the ITT population and historical controls (Overall Historical Control Population: both the UK-PBC Group and Global PBC Study Group databases) on the following outcomes:
	
Clarifies the use of the historical controls as an external control in supportive analyses of the primary endpoint and clarify the process for selecting the comparator group for the primary efficacy analysis using propensity score analysis.


Section	Original Text (Amendment 3, 07 September 2016)	Revised Text (Version 4, 10 May 2017)	Justification for Change
	
 • Time to hepatocellular carcinoma 
(Text from Section 13.1.9 [Alternative Primary Analysis] modified and included in this section)
 
Based on sample size re-estimations, it may be determined that subjects will be enrolled to receive open-label OCA from that point forward, and the new primary efficacy analysis will become the comparison of all subjects in OCA population, to all control subjects (randomized placebo and historical controls) on time to liver transplant or death (all-cause) (see Section 13.1.2.4). similar statistical methodology as specified above in Section 13.1.8 for supportive analyses will be utilized.
 
The propensity score quintile will be then be used as the stratification factor in the stratified log-rank test to compare groups. KM estimates of the distribution of the time to event will be tabulated and graphed by treatment group. The tabulation will include the KM estimate of the medians and corresponding 95% CIs if the medians can be estimated. The number and percent of subjects censored and with events will be presented. The hazard ratio and 95% CI will be determined based on a Cox regression model stratified by randomization strata to estimate the magnitude of the effect.
 
In addition, the outcome events specified above in Section 13.1.8 will also be evaluated to compare all subjects in OCA population to all control subjects (randomized placebo and historical controls).
 
Sensitivity analyses will be conducted limiting to the separate individual historical control databases, ie, UK PBC Group and Global PBC
	
Although the study is designed as a placebo-controlled study, the DMC may recommend changes to study conduct based on the pre-specified interim analyses (see Section 13.1.12), including the potential use of a revised primary efficacy analysis. This analysis would compare all subjects in the OCA population, to all control subjects (randomized placebo and historical controls) on time to liver transplant or death (all-cause), using similar statistical methodology as specified above.
 
Notably, the planned primary analysis would not be revised without prior agreement with regulatory authorities.
	

Section	Original Text (Amendment 3, 07 September 2016)	Revised Text (Version 4, 10 May 2017)	Justification for Change
	Study Group. To evaluate the robustness of the propensity score estimations, additional algorithms and factors may be considered.		

Section 13.1.9 Handling of Dropouts or Missing Data
	
Insertion
	
In addition, the same analyses for primary and key secondary endpoints based on ITT and PP populations will be performed to assess robustness of analysis results. During the conduct of the study, the DMC may recommend refining the missing data strategy to better address the observed pattern of missing data, based on blinded monitoring of the data.
	
Clarification of statistical analyses to address missing data.

Section 13.1.11 Examination of Subgroups
	
The primary and secondary efficacy endpoints will be analyzed for subject subgroups (eg, age, sex, and race) based on the ITT population.
 
Insertion
	
The primary and secondary efficacy endpoints will be analyzed for subject subgroups based on the ITT population.
 
The primary efficacy endpoint will also be assessed across the spectrum of PBC disease stage as defined by Rotterdam criteria (Kuiper 2009)
 
 • Early (normal albumin and normal bilirubin) • Moderate (abnormal albumin or abnormal bilirubin) • Advanced (abnormal albumin and abnormal bilirubin) 
The primary efficacy endpoint will also be assessed for the following clinically relevant subpopulations.
 
 • Monotherapy in patients who are intolerant or non-responsive to UDCA • Elderly patients 
Assuming a strong correlation between biochemistry and clinical outcomes using the
	
Added per Regulatory Authority request.

Section	Original Text (Amendment 3, 07 September 2016)	Revised Text (Version 4, 10 May 2017)	Justification for Change
		
total study population (Section 13.1.5.1) is observed, we will further assess the biochemical improvement in relevant subpopulations as applicable (eg, Rotterdam disease severity and monotherapy) and estimate the reduction in risk of clinical outcomes associated with the biochemical improvement.
 
Additional details regarding statistical methods and subgroup definitions will be provided in the SAP.
	

Section 13.1.12 Continuous Monitoring and Interim Analyses
	
Insertion
	
13.1.12 Continuous Monitoring and Interim Analyses
 
Blinded safety reports including the accrual of events, drop outs, and/or loss of subjects to commercially available OCA will be reviewed by the DMC on a regular basis.
 
Two planned interim analyses of the liver-related outcomes will be conducted using the Lan-DeMets O’Brien-Fleming boundaries (Reboussin 2000). Both interim analyses will be pre-specified and will occur after accrual of 50% (64 events) and 75% (96 events) of clinical outcome events, respectively.
 
The DMC will review the available efficacy data in conjunction with detailed safety data and other relevant information to recommend continuation, modification, or cessation (for efficacy) of the study beyond each interim analysis. Modification of the study would not take place without prior agreement with regulatory authorities.
	
Two Interim Analyses have been added to the protocol.

Section 19 List of References
	
Insertion
	
Beuers U, Gershwin M, Gish R, et al. Changing nomenclature for PBC: From
	
Additional relevant references were added.

Section	Original Text (Amendment 3, 07 September 2016)	Revised Text (Version 4, 10 May 2017)	Justification for Change
		
‘cirrhosis’ to ‘cholangitis’. Digestive and Liver Disease. 2015a;47(11):924-6.
 
Beuers U, Gershwin M, Gish R, et al. Changing nomenclature for PBC: From ‘cirrhosis’ to ‘cholangitis’. Gastroenterology. 2015b;149(6):1627-9.
 
Beuers U, Gershwin M, Gish R, et al. Changing nomenclature for PBC: From ‘cirrhosis’ to ‘cholangitis’. Hepatology. 2015c;62(5):1620-2.
 
 
 
	
Appendix A Modified Dosing Regimen for Subjects with Child-Pugh B or C Hepatic Impairment	Subjects classified as Child-Pugh Class B should eventually titrate to a maximum dose of 5 mg OCA or matching placebo once daily, based on tolerability.	Subjects classified as Child-Pugh Class B should eventually titrate to a maximum dose of 5 mg OCA or matching placebo once daily, based on tolerability and biochemical response.	Rationale 9
Appendix B	This Appendix with the following information has been deleted.		Redundant; Information is contained within the protocol.

Section	Original Text (Amendment 3, 07 September 2016)	Revised Text (Version 4, 10 May 2017)	Justification for Change
List of Study 747-302 Outcome Events	
Several of the specified clinical endpoints will also by definition (see 12.1) qualify as Serious Adverse Events (SAEs). The sponsor must be notified of any SAEs within 24 hours of the site becoming aware of the event (see Section 12.1.4). The Sponsor is responsible for regulatory reporting of SAEs including expeditious reporting of SAEs that are considered related to the investigational product and considered Unexpected by regulatory standards as defined in the Investigational Brochure.
 
The Sponsor may consider the following lists of events to be exempt from expeditious regulatory reporting but will continue to report them in a non-expeditious manner:
 
Potential Clinical Outcome Events:
 
 Liver related events resulting in death Hepatic failure leading to liver transplant Variceal bleed Hepatic encephalopathy Spontaneous bacterial peritonitis Ascites Hepatocellular carcinoma 		
Appendix C Reference Laboratory Values from Central Laboratories	Insertion (new appendix)	Appendix containing reference laboratory values from central laboratories added.	Added per Regulatory Authority request.

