
9.7.3, Assessing Cirrhosis
	
(Insertion)
	
New: 9.7.3. Assessing Cirrhosis
 
To determine which dosing regimen subjects should follow, the presence or absence of cirrhosis should be assessed by the Investigator at Screening Visit 1. Acceptable methods of confirming (via medical history) or assessing cirrhosis for purposes of the study is defined as a subject who has documented evidence or presence of one or more of the following cirrhosis indicators:
 
 • Biopsy results consistent with PBC Stage 4 (Ludwig 1978) • Transient Elastography Median Value ≥ 16.9 kPa (Corpechot 2012) • The presence of any of the following (unless exclusionary per Section 8.3) in the absence of acute liver failure: 
 – Varices – Ascites – Radiological evidence of cirrhosis (nodular liver or enlargement of portal vein and splenomegaly) • Combined low platelet count ($<140\ 000/mm^3$) with: 
 – persistent decrease in serum albumin, or – elevation in prothrombin time /INR (not due to antithrombotic agent use), or – elevated bilirubin ($2\times$ ULN) 
Subjects who exhibit no evidence of cirrhosis by the above methods of assessment will be dosed using the Standard Dosing Regimen, while those who do exhibit evidence of cirrhosis by one or more of the above methods will be dosed using the Modified Dosing Regimen according to their Child-Pugh Score calculated in the electronic case report form (eCRF) (see Appendix A).
 
Cirrhosis status should be reassessed as clinically indicated throughout the study. Any change in
	
Added section to assess cirrhosis as this assessment will determine the acceptable dosing regimen based on a subject's Child-Pugh score.

-----------------------------------	--------------------	--	---

Section	Original Text (Amendment 1.1, 12 November 2015)	Revised Text (Version 3, 07 September 2016)	Justification for Change
		cirrhosis status will necessitate re-evaluation of the dosing regimen.	

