Section	Original Text (Amendment 3, 07 September 2016)	Revised Text (Version 4, 10 May 2017)	Justification for Change

Section 13.1.5 Additional Secondary Efficacy Analyses
	
Insertion
	
Progression to cirrhosis will be assessed in the subset of subjects considered noncirrhotic at Baseline using available medical history, clinical, and laboratory assessments as well as Baseline transient elastography (TE), where available. Specifically, subjects with no clinical, laboratory, or radiological evidence of cirrhosis at baseline and/or a TE liver stiffness of <16.9 kPa (Corpechot 2012) will be considered noncirrhotic. Progression to cirrhosis will be assessed by the development of clinical, laboratory, or radiological evidence of cirrhosis and/or when liver stiffness increases to ≥ 16.9 kPa during the study in which case histological progression to cirrhosis should be confirmed by biopsy unless not medically indicated. Using this definition for progression to cirrhosis, the percentage of noncirrhotic subjects progressing to cirrhosis during the treatment period will be summarized by treatment group and compared using a Cochran–Mantel–Haenszel test stratified by the randomization stratification factor.
 
For those subjects enrolled in the biopsy substudy (defined in Addendum 2) progression to cirrhosis identified by the above criteria and improvement in fibrosis/cirrhosis will be confirmed by paired biopsy. Analyses for the histological assessment conducted as part of the biopsy substudy are defined in Addendum 2.
	
Rationale 11

Synopsis, Statistical
	
Safety data, including AEs, vitals, electrocardiogram, and clinical laboratory results
	
Safety data, including AEs, vitals, electrocardiogram, and clinical laboratory results
	
Clarification of summary analyses.

Section	Original Text (Amendment 3, 07 September 2016)	Revised Text (Version 4, 10 May 2017)	Justification for Change
Methods, Safety Analyses	will compare OCA and placebo using the Safety Population.	will be summarized by treatment group for the Safety Population.	

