	
– Consent may be modified to discontinue study visits or semi-annual telephone contact but allow continued access to medical records to assess for potential adjudicated hepatic and/or cardiovascular events.
 
Subjects who undergo a liver transplant during the course of the study must discontinue investigational product and discontinue the study visit schedule. However, these subjects should be encouraged to consent to the semiannual telephone contact and/or continued record review only to allow for secondary outcome events data to be collected.
	
– Consent may be modified to discontinue study visits or semi-annual telephone contact but allow continued access to medical records to assess suspected major adverse cardiovascular events (MACE) and liver-related clinical outcomes.
 
– Early termination procedures should be conducted if the subject withdraws consent (See Section 9.7.18).
 
The Investigator is encouraged to contact the Sponsor prior to discontinuing a subject from treatment.
					

Section 9.7.1 Visit Windows
	
 
 Screening		
 
	Screening		
 
 Screening	See Section 9.7.6 for scenario specific visit windows that may be applicable at Screening.	
 
	Screening	See Section 9.7.6 for scenario specific visit windows that may be applicable at Screening.	
Screening							
Screening	See Section 9.7.6 for scenario specific visit windows that may be applicable at Screening.						

Section 9.7.3.1 Determination for Dosing Regimen
	
Insertion
 
Acceptable methods of confirming (via medical history) or assessing cirrhosis for purposes of the study is defined as a subject who has documented evidence or presence of one or more of the following cirrhosis indicators:
	
9.7.3.1 Determination for Dosing Regimen
 
Acceptable methods of confirming (via medical history) or assessing cirrhosis for purposes of determining dosing is defined as a subject who has documented evidence or presence of one or more of the following cirrhosis indicators:
	
Header added to differentiate the assessment of cirrhosis for determining dosing regimen versus progression to cirrhosis.
				

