
Section 9.7.3.2 Progression to Cirrhosis
	
Insertion
	
9.7.3.2 Progression to Cirrhosis
 
When a subject identified as noncirrhotic at Baseline per the criteria listed in Section 9.7.3.1 exhibits any signs or symptoms associated with progression to cirrhosis, as defined by the same criteria, the subject should also be assessed by Fibroscan® TE where available and progression to cirrhosis
	
Details the assessment of progression to cirrhosis.
				

Section	Original Text (Amendment 3, 07 September 2016)	Revised Text (Version 4, 10 May 2017)	Justification for Change
		
confirmed by biopsy (centrally read) unless not medically indicated. Laboratory samples needed to obtain noninvasive scores of liver fibrosis (ELF, and aspartate aminotransferase to platelet ratio index [APRI]) will also be collected when a subject develops evidence of progression to cirrhosis.
 
Full instructions concerning the sample collection methods, processing, labeling, and shipping will be provided by the Sponsor in a study-specific histology manual. Collection supplies will be provided by the central laboratory.
 
Sites participating in the paired biopsy substudy must confirm progression to cirrhosis by biopsy as per the information outlined in protocol Addendum 2.
 
All suspected cases of progression to cirrhosis should be submitted for adjudication regardless of the availability of transient elastography or biopsy results.
	

Section 9.7.6 Screening Procedures
	
Two Screening visits will occur from 1 to 8 weeks prior to Day 0 (as outlined below) allowing for the collection of repeated serum chemistry samples (at least 2 weeks apart) to confirm pretreatment ALP and total bilirubin values:
 
Insertion
	
Collection of 2 serum chemistry samples (collected at least 2 weeks apart) during Screening is required for confirmation of the pretreatment serum chemistry values, including the ALP and total bilirubin used to determine eligibility:
 
 • When the 2 bilirubin or ALP assessments collected at Screening Visit 1 and Screening Visit 2 differ by $\geq 30\%$, a third sample must be collected at an unscheduled visit as a confirmatory sample to include in the mean result(s) that will be used to determine eligibility. 	
Allows repeat assessments when baseline laboratory values are discrepant between Screening Visit 1 and Screening Visit 2.

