Liver biopsies will generally be obtained from the right lobe of the liver as described in a study-specific histology manual. If the initial biopsy was obtained from the left lobe, then subsequent biopsies should be obtained from the left lobe, and vice versa.

All biopsy assessments, including screening and histology efficacy assessments, will be performed by study pathologist/central reader blinded to the treatment group assignment. The biopsies will be graded by a central reader using a pre-defined scoring system. Detailed information related to biopsy scoring will be provided to the central reader by the Sponsor in a study-specific histology manual.

Paired biopsies (Screening/Baseline biopsy and post-treatment [or EOT/EOS] biopsy) will be read by a central reader blinded to the treatment group assignment.

Biopsy Criteria for Progression to Cirrhosis

The following criteria will be used for adjudication of progression to cirrhosis:

- Persistent (ie, 2 consecutive measurements obtained at least 3 months apart) elevation in Fibroscan® TE >16.9 kPa, AND/OR
- Presence of any of the following:
 - Gastroesophageal varices
 - Ascites
 - Radiological evidence of cirrhosis (nodular liver or enlargement of portal vein and splenomegaly)
 - Combined low platelet count (<140,000/mm³), with any of the following criteria:
 - Persistent decrease in serum albumin, OR
 - Elevation in prothrombin time/international normalized ratio (not due to antithrombotic agent use), OR
 - Elevated total bilirubin >2x upper limit of normal

Transient Elastography

TE assessment will be performed at the investigational sites, where the device is available, using the Fibroscan instrument (Echosens, Paris, France), to assess liver fibrosis.

Noninvasive Scores of Liver Fibrosis

ELF score will be calculated using an algorithm that combines serum values of tissue inhibitor of metalloproteinases-1, procollagen type-3 N-terminal propeptide, and hyaluronic acid. Likewise, APRI score will be obtained from serum aspartate aminotransferase and platelet values.

ASSESSMENT OF SAFETY

Safety assessments will be performed as in Section 12 of the main protocol. In addition, the Investigator will document her/his opinion of the relationship of the adverse events (AEs) to liver biopsy using the criteria outlined in [Table 2](#).

Table 2: Relationship of Adverse Events to Liver Biopsy

Relationship	Description

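### The baseline noncirrhotic rule in Section 13.1.5 admits subjects whom the protocol's own indicator list calls cirrhotic, and they can later be counted as progressing to cirrhosis

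*Protocol*

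**What the plan says.** The analysis rule is in Protocol Appendix I, Section 13.1.5 (also in the Synopsis; Appendix G shows the same wording for Version 3.1). The at-risk subset is "subjects with no clinical, laboratory, or radiological evidence of cirrhosis at baseline and/or a TE liver stiffness of <16.9 kPa". The sentence before it draws on history, clinical and laboratory data and "Baseline transient elastography (TE), where available". An event is the "development of clinical, laboratory, or radiological evidence of cirrhosis and/or when liver stiffness increases to ≥ 16.9 kPa during the study". For such cases the section then adds a histology step, worded as a recommendation with an exception: "histological progression to cirrhosis should be confirmed by biopsy unless not medically indicated". The percentages progressing are compared with a stratified Cochran–Mantel–Haenszel test.

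The procedures sections use a different baseline rule. Section 9.7.3.1, moved to 7.5.4 in Version 5, calls a subject cirrhotic on "documented evidence or presence of one or more of the following cirrhosis indicators". The list, set out in full in Appendix F, includes "Transient Elastography Median Value ≥ 16.9 kPa", Stage 4 biopsy, varices, ascites and imaging evidence. Section 9.7.3.2, on this same endpoint, opens with "When a subject identified as noncirrhotic at Baseline per the criteria listed in Section 9.7.3.1".

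Two other places describe the event. Section 11.1.2 assesses progression by the presence of evidence. Addendum 2's adjudication criteria also ask for presence of a finding, or for TE above 16.9 kPa on "2 consecutive measurements obtained at least 3 months apart".

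**The concern.** One endpoint has two incompatible baseline rules. Under 13.1.5 a subject needs only one clean result to be at risk. Under 9.7.3.1 and 9.7.3.2 one positive indicator removes the subject. The denominator of the comparison therefore depends on which section the programmer follows, and the rule written in the analysis section is the one that lets in subjects with existing cirrhosis.

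The event rule also joins its two limbs with and/or. A subject who enters with TE of 20 kPa and later shows varices meets it. So does a subject who enters with a nodular liver and TE of 12 kPa and later reaches 17 kPa. Both were already cirrhotic by the protocol's list. Biopsy does not screen them out, because it shows that cirrhosis is there, not that it is new. At stake is the interpretability and power of this secondary comparison.

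**Working it through.** **Step 1: the two baseline rules side by side.** Evidence means clinical, laboratory or imaging evidence.

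| Evidence at baseline | TE at baseline | 13.1.5 (either condition) | 9.7.3.1 (any one indicator) |
|---|---|---|---|
| none | <16.9 | noncirrhotic | noncirrhotic |
| none | ≥16.9 | noncirrhotic | **cirrhotic** |
| present | <16.9 | noncirrhotic | **cirrhotic** |
| present | ≥16.9 | cirrhotic | cirrhotic |
| none | not done | noncirrhotic | noncirrhotic |
| present | not done | cirrhotic | cirrhotic |

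Where TE was done, 13.1.5 admits three of the four combinations and the list admits one. Where TE was not done, the two agree on these markers. Stage 4 biopsy is on the list but is not named in the 13.1.5 rule.

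**Step 2: the only power figures the protocol gives for progression to cirrhosis.** Addendum 2 states 73% and 59% for 45 subjects, about 1:1, one-sided 0.1, placebo rate 0.5 and OCA rate 0.23 or 0.28. The pooled-variance normal approximation with n = 22.5 per arm is

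power = Φ{[(p1 − p2) − z₀.₉·√(2p̄(1 − p̄)/n)] / √([p1(1 − p1) + p2(1 − p2)]/n)}

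- 0.5 vs 0.23: p̄ = 0.365; (0.27 − 1.2816 × 0.1435)/0.1378 = 0.62; power 73.4%.
- 0.5 vs 0.28: p̄ = 0.39; (0.22 − 1.2816 × 0.1454)/0.1417 = 0.24; power 59.4%.

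Both reproduce. The substudy sets baseline status by biopsy, so the 13.1.5 wording does not touch these figures.

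**Step 3: illustration of the dilution.** Let m be the share of the at-risk set already cirrhotic by the list, and q the chance that such a subject is scored as an event, taken as equal in both arms. Neither is in the documents, so both are assumptions. True rates are borrowed from Addendum 2: 0.5 and 0.23.

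Observed rate = (1 − m)·p + m·q

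- m = 0, any q: 1 − 0.23/0.5 = 54% relative risk reduction.
- m = 10%, q = 0.8: 0.9 × 0.5 + 0.08 = 0.530; 0.9 × 0.23 + 0.08 = 0.287; reduction 46%.
- m = 20%, q = 0.8: 0.8 × 0.5 + 0.16 = 0.560; 0.8 × 0.23 + 0.16 = 0.344; reduction 39%.

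| Relative risk reduction | q = 0.5 | q = 0.8 | q = 1.0 |
|---|---|---|---|
| m = 5% | 51% | 50% | 49% |
| m = 10% | 49% | 46% | 44% |
| m = 20% | 43% | 39% | 36% |
| m = 30% | 38% | 32% | 29% |

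The column q = 1.0 is an upper bound. If none were scored (q = 0) the relative reduction would stay at 54%. The risk difference shrinks by the factor (1 − m) whatever q is: 0.27 becomes 0.9 × 0.27 = 0.243 at m = 10% and 0.8 × 0.27 = 0.216 at m = 20%.

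**The case against.** Several points on the other side have force.

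- **Counting is not automatic.** A reader might infer that every subject with existing cirrhosis becomes an event at the first follow-up. Section 13.1.5 does not support that. It asks for evidence that develops, or stiffness that increases to the threshold, so a finding already present at baseline is not an event by itself. A second type of evidence must appear. This stands, and is why q = 1.0 is only a bound. It does not clear the rule, because Section 11.1.2 and Addendum 2 speak of presence and do not ask for onset after baseline.
- **And/or was probably meant for sites without TE.** This is plausible, but the preceding sentence already allows for them, and nothing limits the and/or to them.
- **The indicator list is headed as a dosing rule, and Section 9.7.3.2 already starts the work-up only for subjects clean on that list.** True, but 9.7.3.2 adopts the list for this endpoint. That shows the intended at-risk set and leaves 13.1.5 as the outlier.
- **TE readings.** A reader might infer that one TE reading of 16.9 kPa or more is itself an event in the main study, so that repeated scans produce false events. In 13.1.5 such a reading leads to biopsy unless not indicated, and Section 9.7.3.2 sends all suspected cases to adjudication. It is a trigger, while Addendum 2's persistent reading is an adjudication criterion. What remains is a smaller inconsistency: single versus persistent, and ≥ versus >.
- **Current text.** The Version 6 body is not shown, and the change tables omit minor edits. Version 5 also added a progression-to-cirrhosis algorithm whose content is not shown. That the wording is unchanged is supported but not confirmed.

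**Conclusion.** The point holds as a contradiction between a stated analysis rule and the protocol's own definition of cirrhosis. Where TE was done, 13.1.5 places two groups of already cirrhotic subjects in the noncirrhotic denominator, and they can later be scored as progressing.

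With equal scoring in both arms the result is dilution. A reader might fear bias towards one arm, but under randomization this misclassification does not by itself favour either. Under the borrowed substudy rates and q = 0.8, the relative risk reduction falls from 54% to 46% at a 10% share and to 39% at 20%. Share and scoring probability are both assumed, so the real size cannot be fixed from the documents.

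The endpoint is an additional secondary one. The primary endpoint and the substudy's 73% and 59% power are not affected. This should be fixed, but it does not threaten the trial's main conclusion.

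**What to change.** In Section 13.1.5 and the Synopsis:

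1. Define baseline noncirrhotic for this analysis as none of the Section 7.5.4 indicators present, including Stage 4 biopsy, with TE below 16.9 kPa where TE was done. Replacing and/or by and is not enough, because TE is not available everywhere and biopsy is not named in the present rule.
2. Require the qualifying finding to be new since baseline, and carry that into Section 11.1.2 and Addendum 2, which now ask only for presence.
3. Reconcile the TE criterion between 13.1.5 and Addendum 2 (single or persistent reading, ≥ or >), so that the committee adjudicates one event definition.

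The cost is a slightly smaller at-risk subset and a wording change. No new data are needed. The change is best made before unblinding.
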